## **BACKGROUND**

---

Cleft lip and palate (CLP) is one of the most common congenital abnormalities in the UK with an estimated prevalence of 1 in 700 live births (1, 2). Prevalence varies by ethnicity, geographic origin and gender with males more likely than females to have a unilateral cleft lip and palate (UCLP)(3). In addition a left-sided cleft is more common than a right sided cleft (4). Care of a person with cleft lip and palate is complex. It usually begins with antenatal diagnosis and continues into adulthood. Treatment of cleft lip and palate is resource intensive requiring evaluation and care from a range of specialists including Audiologists, Cleft Nurse Specialists, Clinical Geneticists, Clinical Psychologists, Dieticians, Orthodontists, Medical Photographers, Paediatricians, Paediatric Dentists, Restorative Dentists, Speech and Language Therapists, and Surgeons (from ENT, Plastic Surgery, and Maxillofacial Surgery) to achieve the optimum outcome.

In the 1990s concerns were expressed over the standard of care and outcome in children with cleft lip and palate in the United Kingdom (UK) and the training of those health care professionals providing it (5-8). These concerns led the Clinical Standards Advisory Group (CSAG), to commission a national survey of the care and outcome in children with CLP – referred to in this document as the CSAG survey (9, 10). This survey began in 1996 and ran over a 15 month period. The survey aimed to include all non-syndromic children in the U.K., born with a complete UCLP aged either 5 or 12-years of age. The outcomes assessed included the quality of speech, hearing, naso-labial appearance, dental arch relationships, oral health, the success of alveolar bone grafts (in the 12 year old cohort only) and child/parent satisfaction (11-14).

In 1998 the group published their main report (1). Fifty seven centres were identified as providing a cleft service in the U.K. with the number of cases being treated per year varying considerably. They found that the outcomes of cleft care in the U.K. were generally poor. One of the key findings was the poor outcome with respect to dental arch relationships and profile, when compared with three European centres (Oslo, Bergen, and Nantes). It was reported that 36% of 5 year olds and 39% of 12 year olds with UCLP had a poor dental arch relationship. Other centres in Europe have shown outcomes with less than 10% of UCLP cases having poor dental arch relations (1).

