On the basis of this survey it was concluded that some children with CLP were not receiving optimal care in the UK. The group made nine recommendations to the government all of which were accepted (Appendix 1). The acceptance of these recommendations led to a major reorganization of cleft services across the UK, with the concentration of resources and expertise in fewer units. Current arrangements have configured eleven cleft centres carrying out operations at seventeen cleft sites in the UK working within multi-disciplinary teams.

The overall aim of the current study is to evaluate the impact of this service reorganization on the standard of care currently provided for, and the outcomes achieved in, children with cleft lip and palate in the UK. Centralisation of care in a smaller number of larger centres has important resource and logistic implications for both users and service providers and this study will attempt to estimate the cost and cost effectiveness of the changes in cleft care. The work is funded by a NIHR grant "Evidence based health care for major congenital and acquired problems of the head and neck", Reference Number: RP-PG-0707-10034.

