### **RATIONALE**

---

This survey follows the protocol used in the original CSAG survey which attempted to locate and study all children born with non-syndromic UCLP in defined periods. In addition, the survey will also examine if children with cleft have the same growth development as children without a cleft and examine the psychosocial predictors of outcome such as social and family circumstances, parenting and parental characteristics and child characteristics.

To ensure that we are comparing a similar group of children in the UK, the current study is an observational cross-sectional study of 5-year-olds with UCLP. It is not necessary to survey all children in the UK born with some form of clefting as several multi-centre comparisons have provided evidence that care for and outcomes in, UCLP cases are representative of cleft care across the UK. All of the 5-year-olds born with UCLP in the current study will have been treated within a centralised or centralising service. By the age of 5, children in the UK will have started their formal education and will be speaking to people they are unfamiliar with. Centralized multidisciplinary cleft care teams throughout the U.K. have developed at different rates and have differing models of centralized care. This will allow us to compare differences in the timing of centralisation and a number of different models of care.

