## **STATISTICAL ANALYSIS**

---

We will use multiple linear regression, logistic regression and ordered logistic regression where appropriate to compare the outcomes with those observed in 1998 and to control for confounding factors; this will enable evaluation of the impact of centralisation on outcome of treatment for CLP. We will use multi-level models to explore variations in current practice (including areas such as skin closure techniques, antibiotic use and speech and language therapy) and outcomes across centres.

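### The adjusted comparison with the CSAG survey estimates change over about 15 years, not the impact of centralisation, and the planned timing contrast is not named in the analysis section

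*Protocol*

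**What the plan says.** In the protocol's Statistical analysis section, linear, logistic and ordered logistic regressions are to "compare the outcomes with those observed in 1998 and to control for confounding factors", and the sentence ends with the claim that "this will enable evaluation of the impact of centralisation on outcome of treatment for CLP". The confounders are not listed. A second sentence plans multi-level models for variation in current practice, with examples such as skin closure and speech therapy, and for outcomes across centres.

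The Background section gives the order of events. In the first survey, "Fifty seven centres were identified as providing a cleft service in the U.K". Its report made recommendations to government, and then: "The acceptance of these recommendations led to a major reorganization of cleft services across the UK". The present position is: "Current arrangements have configured eleven cleft centres carrying out operations at seventeen cleft sites in the UK".

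The Rationale of the five-year-old survey says of exposure now: "All of the 5-year-olds born with UCLP in the current study will have been treated within a centralised or centralising service". It adds that teams centralised at different rates and under different models, and concludes: "This will allow us to compare differences in the timing of centralisation and a number of different models of care".

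Objectives 1 and 2 are more modest. They ask for care and outcomes to be described and compared with the first survey.

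**The concern.** The overall aim in the Background section is to evaluate the effect of the reorganisation, and the analysis section rests that on an adjusted before-after difference. The comparison has no concurrent group outside centralised care and no intermediate time point. Anything else that moved between the two surveys is therefore part of the estimate.

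The protocol itself shows some things that may differ with period. The first survey obtained records on 239 of 326 eligible children (73%), and the Study sample section expects fuller capture now because care is better documented. The speech recordings follow a method published in 2009. Untreated caries, one of the outcomes used for the power calculation, can change for reasons unrelated to how cleft services are organised.

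The study's headline conclusion is at stake. A significant difference could be reported as an effect of centralisation, and a null result as its failure, when the comparison supports neither statement. The contrast that does bear on centralisation, between centres that centralised at different times or in different ways, is announced in the Rationale but is not where the analysis section places the claim.

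**Working it through.** **1. The plan's own figures.** Inputs from Power calculations and Study sample: 250 current children, 239 in the first survey, two-sided alpha 0.05, baselines of 40% (arch relations, caries) and 19% (intelligibility), differences of 20 and 10 points. Normal approximation with pooled variance under the null:

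power = Φ[(|p1 − p2| − 1.96·SE0)/SE1], where SE0 = √[p̄(1 − p̄)(1/n1 + 1/n2)] and SE1 = √[p1(1 − p1)/n1 + p2(1 − p2)/n2].

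- 40% v 20%: p̄ = (95.6 + 50)/489 = 0.298, SE0 = 0.0414, SE1 = 0.0405, power 99.8%.
- 19% v 9%: p̄ = (45.41 + 22.5)/489 = 0.139, SE0 = 0.0313, SE1 = 0.0312, power 89.3%.

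The stated values (over 90% and over 80%) hold when the differences are read as improvements.

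**2. What that power detects.** The formula contains two proportions and no cause. Suppose centralisation had no effect and outcomes improved for other reasons. The documents give no trend, so the levels below are assumptions that show how the test behaves. They do not estimate bias.

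| Outcome | Assumed change, other causes only | Chance of a significant result |
|---|---|---|
| Arch relations | 40% to 35% | 21% |
| Arch relations | 40% to 30% | 64% |
| Arch relations | 40% to 25% | 94.5% |
| Arch relations | 40% to 20% | 99.8% |
| Speech | 19% to 14% | 32% |
| Speech | 19% to 9% | 89% |

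**3. Length of the period.** First survey fieldwork began in 1996. Current fieldwork is July 2010 to December 2012. 2010 − 1996 = 14 and 2012 − 1996 = 16, so about 15 years.

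**4. Can regression separate period from centralisation?** Code both before/after. The 239 first-survey rows are (intercept, period, centralised) = (1, 0, 0) and the 250 current rows are (1, 1, 1). The second and third columns are identical, so the rank is 2 for 3 columns. Child or family covariates do not change this, because they do not make those two columns differ.

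**5. If exposure is graded.** Let exposure be zero for all first-survey children and vary across current centres. The rank becomes 3 of 3 (checked with illustrative timings, since the protocol gives no dates). In the model a + b·period + c·exposure, the first-survey rows all have mean a. The period term b absorbs the gap between the cohorts, so c is identified only from differences among current children. Information about centralisation then comes from the current cohort, not from the comparison with the first survey.

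**6. How much is available there?** Timing and model of care vary mainly between 11 centres (17 sites). With an intercept, one timing slope and k models of care (k is not given), about 11 − 1 − 1 − (k − 1) centre-level degrees of freedom remain: 8 if k = 2, 7 if k = 3. Counting sites, 17 gives 14 and 13. The contrast is estimable but imprecise.

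**7. Rationale against Statistical analysis.** The Rationale says timing and models will be compared. The analysis section attaches the centralisation claim to the comparison with the first survey, and its multi-level sentence names neither timing nor model of centralisation.

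**The case against.** The reorganisation was UK-wide, so no concurrent control could exist, and the comparison remains sound for Objectives 1 and 2. This stands. It is a reason to limit the claim, not to abandon the comparison.

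Some change in surgery, training and therapy is the route by which concentrating expertise would act, so it should not all be counted as bias. This also stands. The difficulty is that the comparison cannot say how much of such change came through centralisation.

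Comparability was considered: the survey follows the original protocol and tries not to exclude children the first survey would have included. That helps with case mix and measurement but does not address calendar time.

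The multi-level models could carry timing and model of care as centre-level terms, and a statistical analysis plan, not available here, may say so. A reader might infer that the timing comparison has been abandoned. The protocol does not support that. The two sections do not contradict each other; the analysis section simply does not name the contrast.

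A reader might also infer that the plan codes every current child as fully exposed, and so dilutes the effect by a calculable amount. The protocol does not say how exposure is coded and gives no share of children treated before their centre had centralised. Nor is confounding total across the whole study, because exposure varies within the current cohort. The overlap with period is a property of the comparison with the first survey.

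**Conclusion.** The point holds for the claim attached to the comparison with the first survey. That comparison estimates change in outcome over about 15 years. It cannot attribute the change to centralisation, and no choice of child or family covariates, or later analysis plan, can alter this within the two cohorts. This rests on the protocol's own account that the first survey preceded the reorganisation and that all current children were treated in a centralised or centralising service.

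The size of any misattribution cannot be derived from the protocol, and its direction is not fixed, since other changes could have improved or worsened a given outcome. A reader might infer that centralisation had no effect, or that the difference must overstate it. Neither follows.

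The second part is a mismatch between sections: the contrast announced in the Rationale is not named in the analysis section. With 11 centres and no randomisation, that contrast can support a conclusion about centralisation but not settle it. The stated power figures are correct and unaffected.

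**What to change.** In the protocol's Statistical analysis section, replace the clause on evaluating centralisation with: *this will estimate the change in outcome since the CSAG survey, which may reflect centralisation and other changes over the period.* This agrees with Objective 2.

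In the multi-level model for the current cohort, name two fixed effects: timing of centralisation (for example, years from the centre's or site's centralisation to the child's primary repair, negative if repair came first) and model of care. Report both estimates with intervals, described as supporting, non-randomised evidence on centralisation. Where centralisation was gradual, state how the date was set.

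Limiting the comparison with the first survey to children operated on after centralisation would not serve as a remedy. The period difference would remain, and early-centralising centres might be over-represented.

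Cost: a more modest headline claim and wide intervals. One centralisation date is needed per centre or site (11 or 17). The date of primary repair is also needed; the surgical section draws treatment details from the clinical record but does not list a date among its measures, so it may have to be added if the data form does not already hold it.

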## **POWER CALCULATIONS**

---

In the baseline survey of outcomes in five year old children with CLP nearly 40% had poor dental arch relations; 40% had untreated dental caries and 19% were judged to be impossible to understand or were just intelligible to strangers. With a sample size of 250 children and setting the (2-sided) value of alpha at 0.05 we will have over 90% power to detect an absolute difference in dental arch relations and caries of 20% and over 80% power to detect an absolute difference in intelligible speech of 10%.

